#### **6.2.1 Primary Safety Endpoints**

[figure not shown]
No primary safety endpoint has been defined.

### 6.2.2 Secondary Safety Endpoints

[figure not shown]
Tables displaying incidences of related TEAEs will be provided by system organ class (SOC) and PT for time periods and with table columns as defined at beginning of Section 6.2 above. Related TEAEs in MP and OLEX will also be listed.

CCI

[figure not shown]
CCI

CCI

CCI

[figure not shown]
## 6.4 Special Statistical/Analytical Issues

### 6.4.1 Discontinuations and Missing Data

Main reasons for premature discontinuation of study will be summarized descriptively. As stated in Section 6.2.3, TEAEs leading to discontinuation will be listed. Discontinued subjects will not be replaced.

For subjects discontinuing the study prematurely and for whom end-of-study visit V17 was documented, efficacy data collected at V17 will be analyzed under the study visit which is closest to the recorded V17 date. This will be based on the assessment date relative to (cycle) baseline, and considering treatment received for each cycle, using the following visit windows.

CCI

CCI

For separation of TEAEs from non-TEAEs in case of completely or partly missing start end and time see CCI [REDACTED] Rules for imputation of start dates and start times of AEs are provided in CCI [REDACTED] End dates of AEs will not be imputed.

For worst case imputation of missing causal relationship to treatment, intensity or outcome of an AE refer to [Section 6.2](#). Causal relationship to COVID-19 disease will be listed based on observed cases.

If not otherwise specified, all TEAE analyses will be performed on the SES and all further safety analyses on observed cases.

#### 6.4.2 Interim Analyses

Not applicable.

#### 6.4.3 Multiple Comparisons/Multiplicity

The family-wise two-sided type I error level  $\alpha = 0.05$  for comparisons of treatment groups U and P on the primary and key secondary endpoints will be controlled by a hierarchical test procedure based on two-sided tests with  $\alpha = 0.05$ .

The hierarchical procedure for primary analysis ([Section 6.1.1.1](#)) will be performed as described below. First, using the Mantel-Haenszel test of the null hypothesis that the common difference in response rates at Day 30 is zero, Group U versus Group P will be tested for superiority for proportion of GFL-responders, second for proportion of HFL-responders, and third for proportion of LCL-responders. The test procedure will stop once statistical significance could not be reached.

In case statistical significance can be established for all three primary efficacy endpoints, the procedure will proceed to key secondary endpoints ([Section 6.1.2.1](#)): As next steps, Mantel-Haenszel tests for superiority of Group U versus Group P will be conducted for proportion of subjects with a score of 0 (no) or 1 (mild) on MAS at maximum contraction as assessed by the *investigator* at Day 30 for GFL, then HFL and finally LCL anatomical region. Thereafter, Mantel-Haenszel tests for superiority of Group U versus Group P will be conducted for proportion of subjects with a score of 0 (no) or 1 (mild) on MAS at maximum contraction as assessed by the *subject* at Day 30 for GFL, then HFL and finally LCL anatomical region.

Finally, GAIS as assessed by the *subject* at Day 30 of MP will be tested as described in [Section 6.1.2.1](#).

The hierarchical test procedure will stop once statistical significance could not be reached.

For any other statistical tests on primary or key secondary endpoints (e.g. comparison of treatment groups L and P), no type I error adjustment will be performed. The same accounts for any statistical analyses of further secondary and other endpoints.

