## 5 STUDY OBJECTIVES

The primary objective of this study is to assess the efficacy of simultaneous intramuscular injections of NT 201 in subjects with moderate to severe UFL in comparison to placebo.

The secondary objectives are to assess efficacy and safety of simultaneous single and repeat-dose intramuscular injections of NT 201 in subjects with moderate to severe UFL.

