#### 12.4.7.4 *Multiple comparisons/multiplicity*

The family-wise two-sided type I error level  $\alpha = 0.05$  for comparisons of treatment groups U and P on the primary and key secondary endpoints will be controlled by a hierarchical test procedure based on two-sided tests with  $\alpha = 0.05$ .

The hierarchical procedure for primary analysis (Section 12.4.1.1) will be performed as described below. First, using the Mantel-Haenszel test of the null hypothesis that the common difference in response rates at Day 30 is zero, Group U versus Group P will be tested for superiority for proportion of GFL-responders, second for proportion of HFL-responders, and third for proportion of LCL-responders. The test procedure will stop once statistical significance could not be reached.

In case statistical significance can be established for all three primary efficacy endpoints, the procedure will proceed to key secondary endpoints (Section 12.4.1.2.1): As next steps, Mantel-Haenszel tests for superiority of Group U versus Group P will be conducted for proportion of subjects with a score of 0 (no) or 1 (mild) on MAS at maximum contraction as assessed by the *investigator* at Day 30 of MP for GFL, then HFL and finally LCL anatomical region. Thereafter, Mantel-Haenszel tests for superiority of Group U versus Group P will be conducted for proportion of subjects with a score of 0 (no) or 1 (mild) on MAS at maximum contraction as assessed by the *subject* at Day 30 for GFL, then HFL and finally LCL anatomical region.

Finally, GAIS as assessed by the subject at Day 30 of MP will be tested as described in Section 12.4.1.2.1.

The hierarchical test procedure will stop once statistical significance could not be reached.

For any other statistical tests on primary or key secondary endpoints (e.g. comparison of treatment groups L and P), no type I error adjustment will be performed. The same accounts for any statistical analyses of further secondary and other endpoints.

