### **3 Determination of Sample Size**

Overall, 360 subjects are planned to be randomized to three treatment groups (UFL, LCL or Placebo) with a randomization of 2:1:1 at baseline visit V2.

The FDA required that the clinical development program includes at least 300 completed subjects who are treated simultaneously in all three anatomical areas (GFL, HFL, LCL) under placebo-controlled conditions to support safety. Since two pivotal studies are planned for demonstration of NT 201 efficacy and safety in the combined GFL, HFL and LCL treatment and assuming that up to 15% of the subjects will not complete the study, 180 subjects will be randomized per study to be treated in all three anatomical areas (Group U). A randomization ratio of 2:1:1 for the treatment groups in this study results in 90 subjects for each of the L and P Groups.

These sample sizes provide sufficient power also to assess efficacy under conservative assumptions. For proportions of 20% LCL-responders in Group U and 5% in Group P, a power of 93% is achieved for one-sided Fisher's exact test at  $\alpha = 2.5\%$ . Moreover, if proportions of HFL- and GFL-responders of at least 40% for Group U and at most 5% for Group P are assumed, the samples sizes provide power close to 100%.

In conclusion, when randomizing 180 subjects to Group U and 90 subjects each to Groups L and P, the study will have at least 90% power to establish efficacy of NT 201 using a hierarchical procedure for comparisons of proportions of GFL-, HFL-, and LCL-responders between Groups U and P. Assuming that about 15% of subjects will not complete the MP period, the proposed sample size will result in more than 150 completed subjects in Group U in this study. This number of completed patients in this study is considered sufficient to support the overall safety profile of NT 201 for simultaneous treatment of UFL.

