### 6.1 Efficacy Endpoints and Efficacy Estimands

Primary and sensitivity analyses of primary efficacy endpoints (see [Section 6.1.1.1](#)) and confirmatory analyses of key secondary endpoints will be based on the target population of main primary and key secondary efficacy estimands (see [Section 5.1.1](#) and [Section 5.1.2](#), respectively). It is defined as "Male and female adults (18 years of age or older) with HFL, GFL, and LCL of moderate (score of 2) to severe (score of 3) intensity at maximum contraction as assessed by the investigator and the subject according to MAS, as randomized in this study: Subset of subjects randomized to UFL treatment group or to Placebo treatment group, grouped by randomized treatment assignment.". Further efficacy analyses will be based on the FAS if not otherwise specified. Statistical tests will be two-sided hypothesis tests for between treatment differences in general. Adequate descriptive statistics as specified at the beginning of [Section 6](#) above will be provided for all endpoints.

In case Visit 7/Visit 8 or Visit 12/Visit 13 is performed on same day MAS assessments from Visit 7/Visit 12 will be duplicated to be also analysed and listed at Visit 8/Visit 13.

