### 6.1.1 Primary Efficacy Endpoints and Estimands

[figure not shown]
The primary endpoints will be proportions of GFL-, HFL- and LCL-responders as defined in [Section 5.1.1](#). These proportions will be compared for treatment groups U and P. It should be noted that Group L is not part of the primary efficacy analysis which has the objective to compare efficacy of simultaneous treatment of UFL with NT 201 versus placebo. Group L and Total NT 201 (Group U and Group L pooled) will be considered in the supplementary analyses of primary endpoints on the FAS, the PPS, observed cases in the FAS, observed cases in the PPS (see below), in supplementary analyses of key secondary endpoints, and in analyses of further secondary and other efficacy endpoints.

The three main primary efficacy estimands are defined in [Section 5.1.1](#) (see [CCI](#) for GFL, [CCI](#) for HFL, [CCI](#) for LCL).

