#### 6.1.2.1 Key Secondary Efficacy Endpoints and Key Secondary Efficacy Estimands

Main estimators for key secondary estimands will be calculated for the target population of main key secondary estimands and ICEs will be handled as described in [Section 6.4.6](#).

Main estimators for main key secondary dichotomous MAS-based efficacy estimands ([Section 5.1.2](#)) correspond to main estimators for main primary estimands (see [Section 6.1.1.1](#)). Missing data will be imputed as described in [Section 6.1.1.1](#). For all three anatomical regions and for investigator's as well as subject's assessments on the MAS, stratum-adjusted differences in proportions for overall comparisons of treatment Group U versus Group P (reference) with corresponding 95% Mantel Haenszel CIs and Mantel-Haenszel p-values will be calculated. Responder rates with two-sided 95% Wilson CIs will be provided as well.

Main estimator for the main key secondary estimand based on subject's GAIS [cci](#) will be analysis of covariance with factors treatment group and site, and mean of baseline MAS for HFL, GFL, and LCL at maximum contraction assessed by subject as covariate.

cci

According to the definition of the key secondary estimand based on subject's GAIS [cci](#) specific ICEs will be handled by applying the composite strategy. In these cases, missing subject's GAIS ratings or ratings of [cci](#) (see [Section 6.4.6](#) on ICEs),

regardless of whether the GAIS score from subject assessment at Day 30 (V4) is available or whether it is missing for the respective subject.

Least squares (LS) means, standard error, and two-sided 95% CI per treatment group and LS mean treatment difference ("Group U" – "Group P") with associated two-sided 95% CI and t-Test p-value will be provided. The null hypothesis of this t-Test is that the LS mean treatment difference is zero.

[figure not shown]
CCI

The resulting value will be rounded to two decimals.

Multiplicity adjustment strategy for comparisons of treatment groups U and P on key secondary endpoints is described in [Section 6.4.3](#).

CCI

Results for Group L from any analyses will only be interpreted descriptively.

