#### **6.4.6 Intercurrent Events**

ICEs according to ICH E9 (R1) [1] are prespecified for main primary, supplementary primary, and main key secondary efficacy estimands (see [Section 5.1.1](#), [\[cci\]](#) and [Section 5.1.2](#), respectively) and will be addressed by the handling strategies described in [\[cci\]](#)

CCI

[figure not shown]
In case multiple ICEs with relevance for the same estimand occur for a specific subject, a conservative approach will be adopted for the respective estimand. For example, a composite strategy will be used if this is invoked by at least one of the ICEs relevant for the respective estimand and a treatment policy is used otherwise.

Generally, the above strategies for handling of ICEs will only be applied to estimators for affected estimands. An estimand can only be affected by an ICE if the subject is included

in the target population of the estimand, and only in this case a handling strategy for an identified ICE will be applied.

Likewise, handling strategies for ICEs will not be applied in analyses that are not defined as estimators for any efficacy estimands. This includes, e.g., analyses of primary and key secondary efficacy endpoints on FAS, PPS, observed cases in FAS/PPS and any analyses of further secondary or other efficacy endpoints or any safety or other endpoints.

CCI

CCI

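### Is a confirmatory result wasted because Group L versus placebo stays outside the error-controlled test sequence?

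*SAP*

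**What the plan says.** Protocol 12.4.7.4 and SAP 6.4.3 describe the same fixed sequence and limit family-wise control to U versus P. Steps 1 to 3 are the GFL, HFL and LCL responder rates. Steps 4 to 6 are the investigator's none-or-mild ratings for the three regions, and steps 7 to 9 the subject's. The last step reads: "Finally, GAIS as assessed by the subject at Day 30 of MP will be tested". Tests outside this list are covered by one sentence, with L versus P as its example: "e.g. comparison of treatment groups L and P), no type I error adjustment will be performed". SAP 6.1.2.1 adds: "Results for Group L from any analyses will only be interpreted descriptively".

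The rest of the plan follows the same line:

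- **Objective (Protocol 5).** The primary objective is the efficacy of "simultaneous intramuscular injections of NT 201 in subjects with moderate to severe UFL in comparison to placebo".
- **Confirmatory population (SAP 6.1).** "Subset of subjects randomized to UFL treatment group or to Placebo treatment group".
- **Intercurrent events (SAP 6.4.6).** "handling strategies for ICEs will not be applied in analyses that are not defined as estimators for any efficacy estimands".
- **Where Group L is analysed (SAP 6.1.1).** Group L and the pooled active groups "will be considered in the supplementary analyses of primary endpoints on the FAS, the PPS" and on observed cases. For the further secondary endpoint in the LCL region, SAP 6.1.2.2 also gives L versus P differences.
- **Size of Group L (SAP 3).** The 2:1:1 ratio "results in 90 subjects for each of the L and P Groups". No response rate is given for Group L.

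**The concern.** Group L is randomised, blinded and as large as the placebo group, and its Day 30 ratings are collected and analysed anyway. Yet whatever the data show, the trial cannot formally conclude that NT 201 in the LCL area alone beats placebo. In a fixed sequence run at full alpha, a step placed last is reached only after all others succeed, so it costs the earlier steps nothing. That suggests a confirmatory result is being given away. It could not be recovered later, because a test first declared confirmatory after unblinding is not confirmatory.

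**Working it through.** **1. The sequence.** 3 primary + 6 MAS key secondary + 1 subject's GAIS = 10 tests, all U versus P. LCL appears at step 3 (responders), step 6 (investigator) and step 9 (subject). Under Protocol 8.2, Groups U and L receive the same 24 U in the LCL area.

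**2. The plan's own power figure.** Inputs (SAP 3): 180 in U, 90 in P, LCL response 20% versus 5%, one-sided Fisher's exact test at 2.5%.

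Power = Σₐ Σᵦ Bin(a; n₁, p₁) · Bin(b; n₀, p₀) · 1{Pr(X ≥ a | a + b) ≤ 0.025}, with X hypergeometric.

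The result is 93.5%; the plan states 93%. With a pooled z-test, the mean rate is (36 + 4.5)/270 = 0.15. SE₀ = √(0.15·0.85·(1/180 + 1/90)) = 0.0461 and SE₁ = √(0.16/180 + 0.0475/90) = 0.0376. Then (0.15 − 1.96·0.0461)/0.0376 ≈ 1.58, or 94.3%. The figure is sound.

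**3. Would a last step cost the ten tests anything?** Family-wise error was simulated on idealised normal statistics:

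| Scenario | 10 steps | 11 steps |
|---|---|---|
| No effect anywhere | 0.0499 | 0.0499 |
| Steps 1–3 real, all else null | 0.0505 | 0.0505 |
| Steps 1–10 real, L versus P null | 0 | 0.0496 |

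Simulation error is about 0.0003, so error stays near 0.05 throughout. No decision at steps 1 to 10 changes. This part of the concern is right.

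**4. What could an L versus P test deliver?** Inputs: 90 per group and 5% in P (SAP 3). The Group L rate is an assumption.

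| Assumed L rate | Fisher power, one-sided 2.5% |
|---|---|
| 15% | 54.7% |
| 20% | 84.7% |
| 25% | 96.8% |
| 30% | 99.6% |

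Hand check at 20% with pooled z: SE₀ = √(2·0.125·0.875/90) = 0.0493 and SE₁ = √((0.16 + 0.0475)/90) = 0.0480. Then (0.15 − 1.96·0.0493)/0.0480 ≈ 1.11, or 86.7%. If 15% of subjects count as non-responders (17% versus 4.25%), Fisher power is 76.7%.

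The planned site-stratified Mantel-Haenszel difference with Sato variance was simulated with 12 sites at 20% versus 5%. L versus P succeeds in 89.4% of runs. Step 3 and L versus P both succeed in 87.9%; the Fisher counterpart is 81.5%. With no effect in L and 5% in both groups, the two-sided error of this test is about 5.4% to 5.5%. All power figures ignore the other nine steps, which must succeed as well.

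**5. Does the plan ask this question?**

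- The objectives (Protocol 5, SAP 2) concern simultaneous injections. Protocol 4.2 gives the same aim for the US label.
- Protocol 12.4.1.1 and SAP 6.1.1 give the reason for leaving Group L out of the primary analysis: that analysis compares simultaneous treatment with placebo.
- The multiplicity sections name L versus P as unadjusted, SAP 6.1.2.1 keeps Group L descriptive, and the confirmatory population excludes it.

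These passages agree with one another. No visible objective, hypothesis or sample-size argument calls for a formal test of L against P.

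**The case for a change.** The strongest case for an eleventh step is that it needs no alpha, patients or assessments. At the plan's own conservative LCL rates it would succeed fairly often, and the chance ends at unblinding. All of this is true. It is equally true that the trial as planned cannot formally conclude on LCL treatment alone.

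What does not follow is that the plan falls short. The step would be a new confirmatory claim, and one sentence would not create it. It would need:

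- a matching objective;
- an estimand for subjects randomised to L or P, with intercurrent-event rules, since the present supplementary analyses have none;
- changes to the sentences in SAP 6.4.3 and Protocol 12.4.7.4 that limit control to U versus P and name L versus P as unadjusted, which would otherwise contradict the new step;
- a change to the descriptive-only sentence in SAP 6.1.2.1.

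The SAP follows a protocol version dated 24 June 2021, while the synopsis planned the last primary outcome visit for the second quarter of 2021. Such an amendment would come near or after the planned end of primary data collection, although still before unblinding.

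The purpose of Group L cannot be read in full, because Protocol 6.2 is partly blacked out. Its absence from the visible text is no evidence that the arm is underused.

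**Conclusion.** The concern does not hold. Keeping L versus P descriptive is deliberate, stated in both documents and consistent with the objectives. It changes no error rate, no power figure and no bias in the ten confirmatory tests, and it does not weaken the answer to the trial's own question. The lateral canthal effect of simultaneous treatment is tested three times under error control, with 93.5% power at step 3 under the plan's assumptions. Group L is still analysed, without a confirmatory claim.

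What is forgone is an additional formal statement on LCL treatment alone. Its stand-alone power would be about 55% to over 99% for assumed Group L rates of 15% to 30% against 5% (Fisher, 90 per group), and less for the whole chain. Whether that is worth a new objective, estimand and amendment is a matter of sponsor preference on which statisticians may differ. This conclusion rests on the visible text. It would need another look only if a blacked-out passage made efficacy in the LCL area alone an objective of this trial.

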#### 6.4.4 Examination of Subgroups

Subgroup analyses for the primary efficacy endpoints are specified in [Section 6.1.1.3](#).

Dichotomized endpoints which are based on MAS (assessed by *investigator* and *subject*) for GFL/HFL/LCL at rest will be analyzed in subgroups of subjects with baseline score of at least 2 on the corresponding MAS for GFL/HFL/LCL at rest as assessed by both *subject* and *investigator*. Since scores at rest are in general lower than scores at maximum

contraction, some subjects may have a score of 0 (no) or 1 (mild) at cycle baseline on MAS for GFL/HFL/LCL at rest. These subgroup analyses will be more meaningful and sensitive to treatment effects than analyses of the total FAS as they consider effects in 'symptomatic' subjects, i.e. subjects with 0 (no) or 1 (mild) on corresponding MAS will not be analyzed.

Dichotomized endpoints which are based on IRP assessments on MAS for GFL/HFL/LCL at maximum contraction and at rest will be analyzed in subgroups of subjects with baseline score of at least 2 on the corresponding MAS as assessed by all three raters. These subgroup analyses will be more meaningful and sensitive to treatment effects than analyses of the total FAS as they consider effects in 'symptomatic' subjects, i.e. subjects with 0 (no) or 1 (mild) on corresponding MAS will not be analyzed.

[figure not shown]
#### **6.4.5 Pooling of Sites**

No pooling of sites is planned.

#### **6.4.6 Intercurrent Events**

ICEs according to ICH E9 (R1) [1] are prespecified for main primary, supplementary primary, and main key secondary efficacy estimands (see [Section 5.1.1](#), [\[cci\]](#) and [Section 5.1.2](#), respectively) and will be addressed by the handling strategies described in [\[cci\]](#)

CCI

[figure not shown]
In case multiple ICEs with relevance for the same estimand occur for a specific subject, a conservative approach will be adopted for the respective estimand. For example, a composite strategy will be used if this is invoked by at least one of the ICEs relevant for the respective estimand and a treatment policy is used otherwise.

Generally, the above strategies for handling of ICEs will only be applied to estimators for affected estimands. An estimand can only be affected by an ICE if the subject is included

in the target population of the estimand, and only in this case a handling strategy for an identified ICE will be applied.

Likewise, handling strategies for ICEs will not be applied in analyses that are not defined as estimators for any efficacy estimands. This includes, e.g., analyses of primary and key secondary efficacy endpoints on FAS, PPS, observed cases in FAS/PPS and any analyses of further secondary or other efficacy endpoints or any safety or other endpoints.

CCI

CCI

